3.3 Primary outcome defined using estimands notation

We define 2 co-primary estimands that are the same in all components other than the handling of intercurrent events. Information on the estimator and estimation procedure are given in Section 6.

The estimands for the primary objective are defined as follows:

- (a) the comparison is between Regimen C and Regimen B as defined in Section 1.4;
- (b) the patient population of interest are patients with confirmed RR-TB that meet the inclusion/exclusion criteria as given in the trial protocol, Section 5 (see Section 4.4);
- (c) the endpoint is favourable outcome at Week 76 as defined in Section 3.2;

- (d) the population level summary is the difference in proportions of favourable outcome between treatment arms (See Section 6.1.1). Non-inferiority will be shown if the upper bound of the 2-sided 95% confidence interval of the difference in proportion of favourable outcomes at Week 76 between Regimens B and C is less than the 10% margin of non-inferiority;
- (e) the intercurrent events will be handled as described below.

Intercurrent Event	Strategy for Addressing Intercurrent Event for Primary Estimand 1	Strategy for Addressing Intercurrent Events for Primary Estimand 2
Change of 1 non-major drug in the allocated treatment regimen	Treatment policy strategy: use primary variable regardless of whether or not this intercurrent event had occurred	Treatment policy strategy: use primary variable regardless of whether or not this intercurrent event had occurred
Treatment extension to make up for days when no treatment was given (up to 8 weeks)	Treatment policy strategy: use primary variable regardless of whether or not this intercurrent event had occurred	Treatment policy strategy: use primary variable regardless of whether or not this intercurrent event had occurred
Other changes to allocated treatment regimen (drug substitutions, other treatment extensions, use of salvage regimens)	Composite strategy: occurrence of this intercurrent event is captured in the primary composite variable definition, a participant with this intercurrent event is considered unfavourable	Composite strategy: occurrence of this intercurrent event is captured in the primary composite variable definition, a participant with this intercurrent event is considered unfavourable
Failure to complete a protocol adherent course of allocated treatment	Treatment policy: same as above	Principal Stratum: population is the subgroup of participants who would adhere to treatment, whichever treatment they are allocated
Reinfection	Composite strategy: same as above	Composite strategy: same as above
Death	Composite strategy: same as above	Composite strategy: same as above

4 ANALYSIS POPULATIONS

4.1 Intention-to-treat (ITT)

All randomised patients will be included in the ITT analysis population.

4.2 Safety population

All randomised patients that have taken at least one dose of treatment will be included in the safety analysis population.

4.3 Modified intention-to-treat (mITT)

The mITT population is defined as all randomised patients that have a positive culture for *M. tuberculosis* at screening or randomisation, with the exception of patients with isolates taken before randomisation that are subsequently found to be susceptible to rifampicin, and patients with isolates taken before randomisation that are subsequently found to be

resistant to both fluoroquinolones and second-line injectables (i.e. XDR-TB) on phenotypic DST. Results from the central reference laboratory will take priority over any results from local laboratories where available. Genotypic DST from the central reference laboratory will be used when phenotypic DST is unavailable. Rifampicin susceptible phenotypic DST results will be confirmed by rpoB sequencing. If a participant has rifampicin DST results at screening and randomisation which are discordant they will be considered resistant and included in the mITT population. Participants randomised in error i.e. late screening failures, will be excluded from the mITT population.

4.4 Per protocol (PP)

The PP population will be the same as the mITT population with the exclusion of patients not completing a protocol-adherent course of treatment, other than for treatment failure, change of treatment for an adverse event or death. Treatment failure is defined as failure to attain and maintain culture negativity until the end of allocated treatment.

4.4.1 Definition of a protocol-adherent course of treatment

A patient will have completed a protocol-adherent course of treatment when they have taken 80% of doses within 120% of the duration in both the intensive phase and in the whole treatment period. For this purpose, a dose is defined as all the study medications at the correct dose for that particular day.

For Regimen B and Regimen C, **with or without** an extension of the intensive phase, a patient will have completed a protocol-adherent course of treatment if they have taken 80% of doses within 120% weeks. For example, in participants with no treatment extensions:

- 90 doses (80% of 16 weeks) within 134 days (120% of 16 weeks) in the intensive phase, and
- 224 doses (80% of 40 weeks) within 336 days (120% of 40 weeks) over the whole treatment period (i.e. the combined intensive and continuation phases),
- or in participants with a four week extension:
- 112 doses (80% of 20 weeks) within 168 days (120% of 20 weeks) in the intensive phase, and
- 246 doses (80% of 44 weeks) within 370 days (120% of 44 weeks) over the whole treatment period (i.e. the combined intensive and continuation phases).

For Regimen D, **with or without** an extension of the intensive phase, a patient will have completed a protocol-adherent course of treatment if they have taken 80% of doses within 120% weeks. For example, in participants with no treatment extensions:

- 45 doses (80% of 8 weeks) within 67 days (120% of 8 weeks) in the intensive phase, and
- 157 doses (80% of 28 weeks) within 235 days (120% of 28 weeks) over the whole treatment period (i.e. the combined intensive and continuation phases) with no treatment extensions.

or in participants with a four week extension:

- 67 doses (80% of 12 weeks) within 101 days (120% of 12 weeks) in the intensive phase, and
- 179 doses (80% of 32 weeks) within 269 days (120% of 32 weeks) over the whole treatment period (i.e. the combined intensive and continuation phases).

The same algorithm will apply for Regimen A, the control regimen; the exact number of doses and days depends on the duration of the intensive and continuation phases of Regimen A as implemented locally.

4.5 Modified per protocol (mPP)

Sensitivity analyses for analyses of favourable outcome at Week 76 and Week 132 will use the definition of PP population as specified in version 10.0 of the STREAM protocol, denoted the modified per-protocol population (mPP). Specifically, the mPP population will be the same as the mITT population with the exclusion of patients not completing a protocol-adherent course of treatment, other than for treatment failure or death.

5 GENERAL ANALYSIS PRINCIPLES

Analysis of the primary outcome is described in Section 6. Otherwise, descriptive statistics will be reported overall and by randomised group, and percentages will be of non-missing values, with the number (%) of non-missing values given if data are not complete. Statistical tests will be 2-sided and estimates will be presented with a 2-sided 95% CI. Appropriate transformations for all variables will be applied after inspection of the data. Percentages will be reported to 0 decimal places, unless <0.5% when they will be given to one decimal place. P-values will be given to 2 significant figures.

5.1 Analysis populations

The analyses of the primary outcome will be based on both the mITT and the PP populations for determining non-inferiority. All analyses will be based on the mITT population for determining superiority, with the PP population as a sensitivity analysis. All patients included in the analysis will be analysed in the treatment group to which they were originally randomised.

5.2 Treatment and follow-up phase definitions

For the purpose of analysis, the treatment and follow-up phases for an individual patient will be defined as follows:

Screening phase

- Start: date of screening consent
- o End: day before randomisation

• Treatment phase

- o Start: date of randomisation.
- End: date of last dose of any TB treatment defined as last dose of any TB treatment (including retreatment for relapse), plus 7 days.

• Follow-up phase

- o Start: the day after the end of the treatment phase.
- End: date of the last patient contact (scheduled or unscheduled visit, or other contact e.g. phone call).

The treatment phase includes any extension of treatment or retreatment, and so the Allocated Treatment phase is defined as follows:

• Allocated Treatment phase

- Start: date of randomisation.
- End: date of last dose of trial treatment defined as last dose of allocated regimen or last dose before the addition of a new drug, whichever happens sooner, plus 7 days.

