### 13.1.2 Trial specific exceptions to expedited SAE notification and reporting

Data on disease relapse or progression are collected as part of the primary outcome of the trial and are not considered to be SAEs, unless fatal or in stage 2, requires hospitalisation. QT prolongation does not require grading since the actual QT and QTcF values are collected as part of routine monitoring, but QT or QTcF prolongation to more than or equal to 500 ms should be recorded as a notable event as specified in 13.1.3. Planned hospitalisations for the initial phase of trial treatment are also not considered as SAEs as noted in section 13.1.1 above.

In Stage 2, adverse events which are not serious should be reported on the Stage 2 AE log. However, abnormal laboratory results that are not deemed by the PI to be clinically significant or do not result in change in therapy are exempt from event reporting i.e. they do not need to be added to the AE log. A clinically significant lab value is one that indicates a new disease process, an exacerbation or worsening of an existing condition, or requires further action(s) to be taken.

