This analysis will be conducted on the whole study period, and separately for follow-up censored at Week 76. It will also be repeated comparing bedaquiline and non-bedaquiline regimens (Regimens A and B vs C and D) and comparing Regimen B_{mox} and Regimen C, and Regimen B_{lev} and Regimen C. A descriptive analysis will consider deaths by cause, as adjudicated by an independent review committee. In addition to the comparisons detailed above, analyses of the whole study period (up to Week 132) will include comparisons of Regimen C with Regimen D. Comparisons of Regimen C and Regimen D using data up to Week 76 were carried out at the time of the primary analysis but considered exploratory.

7.2.3 Proportion of patients experiencing a grade 3 or greater adverse event, as defined by the DAIDS criteria, during treatment and follow-up

The difference in proportion of patients experiencing a grade 3 or greater adverse event, as defined by the DAIDS criteria¹⁰, during treatment and follow-up, between Regimen B and Regimen C, between Regimen B_{mox} and Regimen C, between Regimen B_{lev} and Regimen C, between Regimen B and Regimen D, and between Regimen B and Regimen A, with corresponding two-sided 95% confidence intervals and p-values will be estimated (see Section 6.1.1). The analysis will be stratified by randomisation protocol (as defined in Section 1.6) and HIV status with three strata: HIV negative, HIV positive with CD4 count less than 350 cells/mm³, and HIV positive with CD4 count more than or equal to 350 cells/mm³.

This analysis will be conducted on the whole study period, the study period censored at Week 76, and separately for each phase (Treatment censored at Week 76, and Allocated treatment).

Comparisons will be repeated in subgroups according to HIV infection status. In addition the proportion of participants with cardiac events, hearing loss and hepatotoxicity by Week 76 and Week 132 in Regimen C and Regimen D will be compared to Regimen B.

In addition to the comparisons detailed above, analyses of the whole study period (up to Week 132) will include comparisons of Regimen C with Regimen D. Comparisons of Regimen C and Regimen D using data up to Week 76 were carried out at the time of the primary analysis but considered exploratory.

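### In retreated patients the SAP's Treatment phase also covers the off-treatment gap before retreatment, so the phase assigned to an adverse event depends on a later efficacy outcome

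*SAP*

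**What the plan says.** SAP 5.2 opens the Treatment phase with "Start: date of randomisation" and closes it with "End: date of last dose of any TB treatment defined as last dose of any TB treatment (including retreatment for relapse), plus 7 days". The Follow-up phase then has "Start: the day after the end of the treatment phase", so in a retreated patient Follow-up begins only after retreatment has finished.

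The same section recognises that retreatment is included and adds a second phase for that reason: "The treatment phase includes any extension of treatment or retreatment, and so the Allocated Treatment phase is defined as follows". Allocated Treatment ends at "last dose of allocated regimen or last dose before the addition of a new drug, whichever happens sooner, plus 7 days".

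SAP 7.2.1 places adverse events in phases by start date. SAP 5.8 calls an event treatment-emergent in a phase if it is worse than baseline; the patient need not be taking treatment at the time. SAP 7.2.3 analyses grade 3 or higher events over the whole study, over the study censored at Week 76, and "separately for each phase (Treatment censored at Week 76, and Allocated treatment". SAP 9.3.5 uses the whole study and the same two phases for the SAE, notable event and AE tables. Protocol 13.1.2 excludes disease relapse from SAE reporting "unless fatal or in stage 2, requires hospitalisation".

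**The concern.** The phase is one unbroken interval whose end is fixed by the last course of treatment, whenever that occurs. Take two patients who finish allocated treatment on time and each have the same grade 3 event at Week 50, off all TB drugs. If one is later retreated, that patient's event is a Treatment event. The other patient's is a Follow-up event. Nothing about the event or about exposure at the time differs. The label comes from a later efficacy outcome.

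The gap is also where a deterioration that leads to retreatment would occur. A relapse admission in Stage 2 is an SAE. If it comes before the first retreatment dose and before the Week 76 cut, it is tabulated under Treatment.

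At stake is how the Treatment tables are read. An arm with more retreatment contributes more off-treatment time and more relapse-related events to them, so part of an efficacy difference can appear as a difference in events during treatment. A shorter regimen leaves room for a longer gap, and Regimen D against Regimen B is a planned comparison in SAP 7.2.3.

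**Working it through.** The plan states no figure on this point, so there is nothing to reproduce. The check has two parts: days, from the SAP's definitions, and percentage points, from assumed rates.

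**1. Off-treatment days placed in the Treatment phase**

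Inputs: planned duration is 40 weeks for Regimens B and C and 28 weeks for Regimen D (SAP 1.5); the tail is 7 days (SAP 5.2); randomisation is study day 1, the Week 76 target is day 533 and its window ends on day 574 (SAP 5.3). The SAP does not say which of these two days is the Week 76 cut, so both are used. The week in which retreatment starts is assumed.

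- End of Allocated Treatment = 7 × weeks + 7. B/C: 280 + 7 = day 287. D: 196 + 7 = day 203.
- Gap = the smaller of (last day before retreatment, cut day), minus the end of Allocated Treatment.

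| Retreatment starts | B/C, days | D, days |
|---|---|---|
| Week 52 (last day before: 364) | 77 | 161 |
| Week 60 (420) | 133 | 217 |
| Week 68 (476) | 189 | 273 |
| After the cut, cut at day 533 | 246 | 330 |
| After the cut, cut at day 574 | 287 | 371 |

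The last two rows apply the phase end as SAP 5.2 defines it and then cut at Week 76. Retreatment that starts after Week 76 then turns all off-treatment time up to the cut into Treatment.

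Averaged over an arm, if 2% to 15% are retreated from Week 60 (assumed):

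- B/C: 0.02 × 133 = 2.7 to 0.15 × 133 = 20 days per patient, or 0.9% to 7.0% of 287 days.
- D: 0.02 × 217 = 4.3 to 0.15 × 217 = 33 days per patient, or 2.1% to 16% of 203 days.

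**2. Effect on the proportion with a grade 3 or higher event**

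Assumed, since the documents give none of these: fraction retreated f = 0.03 to 0.08; gap g = 15 to 25 weeks; background hazard h = 0.003 to 0.006 per off-treatment week; probability p = 0.3 to 0.5 that a relapse brings a grade 3 or higher event or an admission before retreatment.

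- Background only: f × (1 − exp(−h × g)). Low: 0.03 × 0.044 = 0.13 points. High: 0.08 × 0.139 = 1.11 points.
- Relapse-related only: f × p. Low: 0.03 × 0.3 = 0.9 points. High: 0.08 × 0.5 = 4.0 points.
- Either: f × [1 − (1 − p) × exp(−h × g)]. Low: 0.03 × 0.331 = 0.99 points. High: 0.08 × 0.570 = 4.56 points.

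These figures are too high for this outcome, because a patient who already had a grade 3 or higher event during allocated treatment adds nothing. Stage 1 reported 48.2% with such an event on Regimen B over treatment and follow-up (Protocol 2.1.1). If 30% to 48% already had one (assumed), multiply by 0.70 to 0.52:

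- One arm, low: 0.99 × 0.52 = 0.5 to 0.99 × 0.70 = 0.7 points.
- One arm, high: 4.56 × 0.52 = 2.4 to 4.56 × 0.70 = 3.2 points.
- Difference between arms, if one has 4 points more retreatment (assumed): 0.04 × 0.331 × 0.52 = 0.7 to 0.04 × 0.570 × 0.70 = 1.6 points.

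Total event counts in SAP 9.3.5 are not reduced in this way, because repeat events in one patient still count.

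**The case against.** The strongest reply is that the SAP saw the issue and dealt with it. Straight after the definition it says that retreatment is included, and it defines Allocated Treatment for that reason. That phase excludes the gap, the pre-retreatment admission and the retreatment, and it is reported beside Treatment in both places. Grade 3 or higher events over treatment and follow-up, the same analysis censored at Week 76, and the mortality analyses do not use the phase boundary. This stands, and it confines the problem to one set of supporting results.

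A reader might infer that the trial's main tolerability comparison is biased against the arm with more relapses, or that relapses are counted as on-treatment toxicity. The documents do not support that. The SAP never calls this phase on-treatment and does not name it as the tolerability analysis. Nothing says that a relapse admission comes before the first retreatment dose. Events after the Week 76 cut are not in the table at all. Regimens B and C have the same planned duration, so a bias between them needs unequal retreatment. Regimen D comparisons are secondary, with about 100 patients anticipated (Protocol 11.4.3), so 1 point there is about one patient.

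Two limits apply to the reply. First, Allocated Treatment is not a full substitute: it also stops when a new drug is added, and SAP 3.2 allows replacement of a single drug without an unfavourable outcome. A patient with such a replacement leaves that phase while still on most of the regimen. Neither reported phase is exactly the time on TB treatment. Second, an unaffected companion table does not make the label on the affected one correct.

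It could also be said that a Week 76 analysis would derive the phase only from doses given before the cut. If so, retreatment after Week 76 would have no effect, but retreatment before it still would. The SAP does not say.

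**Conclusion.** The point holds as a narrow error in a phase definition. SAP 5.2 states a rule that, in retreated patients, assigns off-treatment events before retreatment to Treatment, and so makes the phase depend on a later outcome. It affects only the results for Treatment censored at Week 76.

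On the assumed rates, the effect on the proportion with a grade 3 or higher event is probably about 1 point and at most about 2 to 3 points. These sizes rest on assumed retreatment, hazard and relapse-event rates and on an assumed share of patients already counted. The day counts rest only on the SAP's definitions and the assumed week of retreatment. This is a minor point: it does not touch the primary endpoint or the whole-study safety conclusions.

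**What to change.** In SAP 5.2, define the Treatment phase as the periods actually on TB treatment: end it 7 days after the last dose of each course, restart it on the first day of retreatment, and assign events that start in the gap to Follow-up. For retreatment from Week 60 this removes 133 days per retreated patient in B/C and 217 in D.

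Name Allocated Treatment as the main on-treatment tolerability summary. This is needed because the revised Treatment phase still includes retreatment weeks and salvage-regimen toxicity, so observation time would remain unequal between arms with different retreatment. State also whether the Week 76 cut is day 533 or day 574.

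The cost is a change of wording and minor reprogramming of phase assignment, using treatment dates that the present definition already needs. Follow-up is not a separately reported phase in SAP 7.2.3 or 9.3.5, so reassigned events would appear only in results that do not use the phase boundary, unless a Follow-up table is added. If reprogramming is not wanted, the minimum is to title the present table as running to the end of any TB treatment, including retreatment.

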5.3 Visit window definitions

In Stage 2, patients will be assessed at screening, randomisation (Week 0), Week 1, Week 2, Week 3, Week 4, after which they will be seen 4-weekly until Week 52, after which they will

be seen 8-weekly until Week 84, after which they will be seen 12-weekly until Week 132 post randomisation.

Baseline is defined as the date of randomisation (Study day 1). For all variables the baseline measurement will be the one taken at the randomisation visit. If this does not exist the measurement from the screening visit will be used if available. For ECG measurements, the mean of all available measurements from the randomisation visit will be used.

For the purpose of analysis, each scheduled visit will have a window before and after the target date, calculated from date of randomisation. When referring to a visit hereon, this implies within the defined visit window as specified below in Table 2.

Table 1: Visit window definitions

Visit	Target study day	Analysis window (study days)
Screening /	1	Date of screening consent – 1
Baseline		
Week 4	29	2-42
Week 8	57	43-70
Week 12	85	71-98
Week 16	113	99-126
Week 20	141	127 – 154
Week 24	169	155 – 182
Week 28	197	183 – 210
Week 32	225	211 – 238
Week 36	253	239 – 266
Week 40	281	267 – 294
Week 44	309	295 – 322
Week 48	337	323 – 350
Week 52	365	351 – 392
Week 60	421	393 – 448
Week 68	477	449 – 490
Week 76	533	491 - 574*
Week 84	589	575 – 630
Week 96	673	631 – 714 [†]
Week 108	757	715 – 798†
Week 120	841	799 – 882†
Week 132	925	883 – no upper bound [†]

NB. Study day 1 =date of randomisation

Any visit, scheduled or unscheduled, that falls into the analysis window will be assigned to that visit for the purpose of analysis. If two visits fall within the same interval, the one closest to the target date will be used for analyses by visit, so that there is only one unique visit for each patient and analysis time-point.

^{*} see section 3.1.1

[†] see section 5.3.1

There are additional study visits at Weeks 1, 2 and 3 only for ECG monitoring. For the analysis of ECG data only, there will be additional visit windows: Week 1 (2-11), Week 2 (12-18), Week 3 (19-25) and the Week 4 visit window will be modified to (26-42).

